4.10 Duration of Follow Up

The Follow-Up Phase begins when the decision to discontinue a subject from study therapy is made (no further treatment with study therapy).

All subjects who discontinue investigational product should comply with protocol specified follow-up procedures as outlined in Section 10, Study Calendar.

A mandatory End of treatment (EOT) visit (+/- 7 days) should be performed 28 days after the last dose of study drug(s).

After completion of the EOT visit, subjects will be followed every 3 months for survival.

Subjects who are discontinued from the study treatment due to an unacceptable toxicity will be monitored for safety until the resolution of the AE to \leq grade 1 or stabilization or until initiation of a new therapy for their cancer, whichever occurs first.

SAEs will be collected and recorded throughout the study period, from the first dose of the investigational agent through 100 days (+ 14 days) after the last dose of study drug or end of the study (if thought to be related to study drug), or 30 days after the initiation of a new anticancer therapy, whichever is earlier.

5. DOSING DELAYS/DOSE MODIFICATIONS

In order to maintain dose-intensity and cumulative dose-delivery on this study, reasonable efforts will be made to minimize dose reduction and treatment delays as specified below.

Although entinostat and immune checkpoint blockade have distinct toxicity profiles, they do share some adverse events such as fatigue, nausea and diarrhea. There is the theoretical possibility that one agent may potentiate the other and hence drug causality will not always be clear. In the event of uncertainty, dose reductions and/or delays will follow the most conservative approach.

For any event which is apparent at baseline, the dose modifications will apply according to the corresponding shift in toxicity grade, if the investigator feels it is appropriate (e.g., if a subject has grade 1 asthenia at baseline which increases to grade 2 during treatment, this will be considered as a shift of 1 grade and treated as a grade 1 toxicity for dose modification purposes).

All toxicity grades below are described using the NCI Common Terminology Criteria for Adverse Events (CTCAE) version 4.03.

All discontinuations, relationships to treatment, and treatment decisions must be clearly documented in the medical record. Any questions should be discussed with the IND Sponsor.

Dose reductions due to toxicity are permanent. Dose escalation is not allowed. Dose reduction is not allowed for Nivolumab treatment.

NOTE: Tumor assessments should continue as per protocol even if dosing is delayed.

5.1 Dose Criteria

Entinostat

Prior to administration of first dose of entinostat in each cycle, subject's organ function and treatment-related toxicities must have recovered to the following values:

- Absolute Neutrophil Count (ANC) \geq 1,000 x 106/L
- Platelets \geq 75,000 x 106/L
- Creatinine $\leq 1.5 \text{ x ULN OR} > 60 \text{ mL/min}$ for patient with creatinine levels $>1.5 \times$ institutional ULN.
- Non-hematologic toxicities ≤ Grade 2 as noted below for entinostat-related toxicity Nivolumab

Dosing of nivolumab will be delayed for any of the criteria listed below:

- Total bilirubin $\geq 1.5 \times ULN$ (for patients with diagnosed Gilbert's Syndrome, direct bilirubin should be within normal institutional limits).
- Aspartate aminotransferase (AST) and alanine aminotransferase (ALT) > 3 ×ULN **OR** ≥5 ×ULN for patients with liver metastases: NOTE appropriate evaluation for autoimmune transaminitis must be conducted
- Any ≥ Grade 2 non-skin, non-laboratory, drug-related adverse event, with the following exception:
- Grade 2 drug-related fatigue does not require a treatment delay.
- Grade 2 hypothyroidism or thyroiditis does not require a treatment delay

- Subjects with Grade 3 thyroiditis or hypopituitarism may be restarted with replacement hormones including thyroid hormone and physiologic doses of corticosteroids. NOTE: grading for hypophysitis with symptoms of headache, visual or neurologic changes or radiologic evidence of pituitary enlargement and other CNS events such as aseptic meningitis or encephalitis should be considered grade 3 events
- Any \geq Grade 3 skin, drug-related adverse event.
- Any \geq Grade 3 drug-related laboratory abnormality with the following exceptions:
- Grade 3 lymphopenia does not require dose delay
- Any Grade \geq 3 drug-related amylase or lipase abnormality that is not associated with symptoms or clinical manifestations of pancreatitis does not require dose delay.
- Isolated grade 3 or 4 electrolyte imbalances/abnormalities that are not associated

[figure not shown]

with clinical sequelae and are corrected with supplementation/appropriate management.

• Any adverse event, laboratory abnormality, or intercurrent illness which, in the judgment of the investigator, warrants delaying the dose of study medication

[figure not shown]
If the criteria to resume treatment are met, the patient should restart treatment no sooner than the next scheduled time point per protocol. However, if the treatment is delayed past the next scheduled time point per protocol the treatment should resume at the earliest convenient point that is within the six week delay period.

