5.1.4 Nivolumab Treatment Discontinuation

Nivolumab treatment should be discontinued if any of the following criteria are met:

- Any Grade 2 treatment-related uveitis, eye pain, or blurred vision that does not respond to topical therapy and does not improve to Grade 1 severity within 2 weeks of starting therapy requires systemic treatment
- Any Grade 3 non-skin, drug-related AE lasting > 7 days, with the following exceptions:
 - Grade 3 treatment-related uveitis, pneumonitis, bronchospasm, diarrhea, colitis, neurologic toxicity, hypersensitivity reaction, or infusion reaction of any duration requires discontinuation
 - Grade 3 treatment-related endocrinopathies (except for adrenal insufficiency) adequately controlled with only physiologic hormone replacement DO NOT require discontinuation
 - Grade 3 fatigue that lasts >14 days
- Grade 3 treatment-related thrombocytopenia > 7 days OR that is associated with bleeding requires discontinuation
- Any treatment-related liver function test (LFT) abnormality that meets the following criteria, require discontinuation:
 - Total bilirubin $> 5 \times ULN$
 - Concurrent AST or ALT \ge 3 × ULN and total bilirubin > 2 × ULN
- Any treatment-related liver function test (LFT) abnormality that meets the following criteria, require discontinuation:
 - AST or ALT >5 x ULN in patients with AST/ALT level within normal limits at baseline
 - AST or ALT >10 \times ULN in patients with AST/ALT level more than 1 and up to 3 times ULN at baseline
 - Total bilirubin >3 x ULN irrespective of baseline levels

- Concurrent AST or ALT \geq 3 \times ULN and total bilirubin > 2 \times ULN, irrespective of baseline levels
- Any Grade 4 treatment-related AE or laboratory abnormality, except for the following events which DO NOT require discontinuation:
 - Grade 4 amylase or lipase abnormalities that are not associated with symptoms or clinical manifestations, or radiographic signs of pancreatitis.
 - Isolated grade 4 electrolyte imbalances/abnormalities that are not associated with clinical sequelae and are corrected with supplementation/appropriate management within 72 hours of their onset.
 - Grade 4 lymphopenia and leukopenia.

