 - Grade 4 treatment-related endocrinopathy adverse events, such as ACTH deficiency, hyper- or hypothyroidism, or glucose intolerance, which resolve or are adequately controlled with physiologic hormone replacement (corticosteroids, thyroid hormones) or glucose-controlling agents, respectively, may not require discontinuation after discussion with and approval from the Sponsors.
- Grade 3 and 4 adrenal insufficiency require discontinuation
- Any dosing interruption lasting >6 weeks, with the following exceptions: NOTE: Dosing interruptions >6 weeks that occur for non-drug-related reasons as well as for treatment of related AEs and subsequently tapering of steroids may be allowed if approved by the IND Sponsor. Patients must have had no recurrence of symptoms or new symptoms during steroid taper.

New immune related events or exacerbation of existing events during steroid treatment or taper suggest the presence of ongoing immune activation and should require permanent discontinuation.

• Any subjects who require additional immune suppressive treatment beyond steroids should go off study treatment

If nivolumab has to be permanently discontinued because drug-related toxicity, the patient will be permanently discontinued from entinostat treatment too.

In the case that a participant develops intolerance or side effect that is attributable to entinostat, the participant may, at his or her discretion, continue to receive only Nivolumab as otherwise indicated as long as they have received at least 1 full dose of both entinostat and nivolumab and nivolumab re-treatment criteria are met as outlined above.

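### The nivolumab restart and stop rules give opposite dispositions for adrenal insufficiency caused by pituitary or ACTH failure; secondarily, the AST/ALT hold and stop limits are set on different strata

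*Combined protocol and SAP*

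**What the plan says.** **Endocrine events.** In the nivolumab part of Section 5.1 (Dose Criteria), the delay list includes a restart allowance: "Subjects with Grade 3 thyroiditis or hypopituitarism may be restarted with replacement hormones including thyroid hormone and physiologic doses of corticosteroids". Section 5.1.4 (Nivolumab Treatment Discontinuation) then has three relevant bullets:

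- Grade 3 exception: "Grade 3 treatment-related endocrinopathies (except for adrenal insufficiency) adequately controlled with only physiologic hormone replacement DO NOT require discontinuation".
- Grade 4 exception: "Grade 4 treatment-related endocrinopathy adverse events, such as ACTH deficiency, hyper- or hypothyroidism, or glucose intolerance", if resolved or controlled on physiologic replacement (corticosteroids are named) or glucose-controlling agents, "may not require discontinuation after discussion with and approval from the Sponsors".
- The bullet that follows: "Grade 3 and 4 adrenal insufficiency require discontinuation". It carries no exception, no approval route and no distinction by cause.

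**AST/ALT.** Section 5.1 delays nivolumab when AST *and* ALT exceed 3 × ULN, or at "≥5 ×ULN for patients with liver metastases", and asks for an evaluation for autoimmune transaminitis. Section 5.1.4 stops nivolumab for treatment-related abnormalities only: "AST or ALT >5 x ULN in patients with AST/ALT level within normal limits at baseline", or above 10 × ULN when baseline was more than 1 and up to 3 × ULN.

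**Consequence of a stop.** Section 5 does not allow nivolumab dose reduction. Sections 4.8 and 5.1.4 both say that a permanent nivolumab stop for drug-related toxicity also ends entinostat.

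**The concern.** One endocrine picture can be recorded as hypopituitarism, as ACTH deficiency or as adrenal insufficiency. Under the first two terms the plan permits continued or resumed nivolumab; under the third it requires a permanent stop. The plan does not say which term governs when more than one applies, so two patients with the same event could be managed differently, and for one of them both drugs would end.

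The AST/ALT rules raise a lesser question. Nivolumab cannot be reduced, so a hold is the only dosing step short of stopping. Holding and stopping are keyed to different patient characteristics, and in one combination of these the hold step almost disappears.

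At stake are patient safety, uniform dosing and the meaning of the reported reasons for discontinuation.

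**Working it through.** The plan gives no figure to reproduce on this point. The check sets the rules side by side.

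**Endocrine rules**

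| Event as classified | Rule allowing nivolumab | Rule stopping nivolumab | Result |
|---|---|---|---|
| Grade 3 hypopituitarism, no adrenal insufficiency, controlled on replacement | 5.1 restart; 5.1.4 Grade 3 exception | none | consistent |
| Grade 3 hypopituitarism, also classed as adrenal insufficiency | 5.1 restart | 5.1.4 carve-out and stop bullet | opposite |
| Grade 4 ACTH deficiency, controlled, not classed as adrenal insufficiency | 5.1.4 Grade 4 exception, with approval | none | consistent |
| Grade 4 ACTH deficiency, also classed as adrenal insufficiency | 5.1.4 Grade 4 exception, with approval | 5.1.4 stop bullet | opposite |

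The sharpest conflict lies between two adjacent bullets of 5.1.4, at Grade 4. The text itself makes the overlap plausible: both the 5.1 sentence and the Grade 4 exception name corticosteroids among the replacement hormones.

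**AST/ALT rules**

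Let v be the enzyme value in multiples of ULN. Take AST = ALT, a treatment-related rise and bilirubin not raised.

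- Hold (5.1): v > 3 without liver metastases; v ≥ 5 with them.
- Stop (5.1.4): v > 5 if baseline was normal; v > 10 if baseline was >1 to 3.
- Hold-only range: values that meet the hold rule and not the stop rule.

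| Liver metastases | Baseline AST/ALT | Hold-only range | Width |
|---|---|---|---|
| No | normal | >3 to 5 | 5 − 3 = 2 |
| No | >1 to 3 × ULN | >3 to 10 | 10 − 3 = 7 |
| Yes | normal | exactly 5 | 5 − 5 = 0 |
| Yes | >1 to 3 × ULN | 5 to 10 | 10 − 5 = 5 |

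Stepping v from 1.0 to 13.0 by 0.1 gives 20, 70, 1 and 51 hold-only values in these four rows. Section 3.1.5 admits patients with AST/ALT up to 3 × ULN, so the raised-baseline rows are real strata.

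If the rise is not treatment-related, the AST/ALT stop limits do not apply. The hold bullet has no such restriction, so these patients are held without being stopped.

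**Connectors**

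Suppose baseline is normal, one enzyme is above 5 × ULN and related to treatment, and the other is at or below 3 × ULN. The stop rule (*or*) is met. The AST/ALT hold bullet (*and*), read literally, is not.

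**The case against.** The strongest reply on the endocrine side is that the documents never say that ACTH deficiency is, or causes, adrenal insufficiency. They name the two separately, the Grade 3 carve-out is explicit, and the restart sentence in 5.1 is only permissive. Sponsor contact is also built in: Section 4.5.1 asks for immediate discussion of drug-related events of Grade 2 or higher, and Section 5 sends questions to the IND sponsor. Part of this stands. The overlap is a clinical reading, and without it there is no conflict. But consultation settles single cases and does not say which bullet governs. The conservative-approach sentence in Section 5 does not settle it either: it concerns uncertain drug causality and covers reductions and delays, not discontinuation.

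On the liver side, equal hold and stop limits do not give opposite instructions. Dosing can be held while the cause is established and stopped if the rise is drug-related. That stands, and this part is a mismatch, not a contradiction. The *and*/*or* difference is partly covered by other hold bullets in 5.1, for drug-related laboratory abnormalities of Grade 3 or higher and for investigator judgment. *And* may also simply name two tests.

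The content of 5.1.3 and the hepatic and endocrine algorithms of Appendix D are not visible here and may show the intent. Their absence from this copy is not a fault of the plan. Even if they settle the intent, the wording of 5.1 and 5.1.4 would still need to match it.

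**Conclusion.** The endocrine inconsistency holds, on the assumption that one event can be classed both as pituitary or ACTH failure and as adrenal insufficiency of Grade 3 or 4. Under that classification the plan both permits and forbids further nivolumab, and the forbidding rule takes entinostat with it. The AST/ALT point is secondary: the limits coincide in one of four strata, and only for treatment-related rises.

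Three stronger readings are tempting and are not supported:

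- *Patients with liver metastases have no hold range.* With raised baseline, 5 to 10 × ULN remains, and rises unrelated to treatment are held without a stop.
- *The affected stratum is the commonest patient type.* Section 9.2.1 says only that biopsies will probably be of liver. It gives no share of patients by metastases and baseline enzymes, and the documents give no rate for the endocrine events.
- *The response decision in Section 12.2 (4 or more of 27) could turn on this.* Under Sections 8.2 and 12.3.1 patients stay evaluable after one entinostat dose, so a stop does not remove them from the denominator. Any effect through lost treatment is indirect and cannot be sized.

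The grounds for acting are patient safety and uniform dosing.

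**What to change.** The sponsor should reconcile 5.1 and 5.1.4 with each other and with 5.1.3 and Appendix D:

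- Give adrenal insufficiency due to pituitary or ACTH failure one disposition, and use it in the 5.1 restart sentence, in both endocrine exceptions of 5.1.4 and in the adrenal insufficiency bullet.
- Use the same connector for AST and ALT in the hold and stop rules.
- Set the hold and stop limits on consistent strata. If the coincidence for liver metastases with normal baseline is intended, say so.

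Which disposition, limit or connector applies is for the clinical team. The cost is a short wording amendment with the IRB approval that Section 11.3 requires. The sample size and the analysis do not change.

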5.1.1 Entinostat Dose Adjustments

[figure not shown]

Phase 2 Study Of Entinostat and Nivolumab in Unresectable or Metastatic Cholangiocarcinoma and Pancreatic Adenocarcinoma Principal Investigator: [name].

[figure not shown]
5.1.2 Discontinuation of Entinostat Treatment

Entinostat treatment should be discontinued if any of the following criteria are met: • For any grade 4 toxicity that recurs despite prophylaxis or dose reduction

• Any adverse event, laboratory abnormality, or intercurrent illness which, in the judgment of the investigator, presents a substantial clinical risk to the subject with continued study drug dosing

[figure not shown]

[figure not shown]
5.1.3 Nivolumab Dose Managements

Phase 2 Study Of Entinostat and Nivolumab in Unresectable or Metastatic Cholangiocarcinoma and Pancreatic Adenocarcinoma Principal Investigator: [name].

[figure not shown]

Phase 2 Study Of Entinostat and Nivolumab in Unresectable or Metastatic Cholangiocarcinoma and Pancreatic Adenocarcinoma

[figure not shown]

[figure not shown]
Principal Investigator: [name].

[figure not shown]

Phase 2 Study Of Entinostat and Nivolumab in Unresectable or Metastatic Cholangiocarcinoma and Pancreatic Adenocarcinoma Principal Investigator: [name].

5.1.4 Nivolumab Treatment Discontinuation

Nivolumab treatment should be discontinued if any of the following criteria are met:

- Any Grade 2 treatment-related uveitis, eye pain, or blurred vision that does not respond to topical therapy and does not improve to Grade 1 severity within 2 weeks of starting therapy requires systemic treatment
- Any Grade 3 non-skin, drug-related AE lasting > 7 days, with the following exceptions:
 - Grade 3 treatment-related uveitis, pneumonitis, bronchospasm, diarrhea, colitis, neurologic toxicity, hypersensitivity reaction, or infusion reaction of any duration requires discontinuation
 - Grade 3 treatment-related endocrinopathies (except for adrenal insufficiency) adequately controlled with only physiologic hormone replacement DO NOT require discontinuation
 - Grade 3 fatigue that lasts >14 days
- Grade 3 treatment-related thrombocytopenia > 7 days OR that is associated with bleeding requires discontinuation
- Any treatment-related liver function test (LFT) abnormality that meets the following criteria, require discontinuation:
 - Total bilirubin $> 5 \times ULN$
 - Concurrent AST or ALT \ge 3 × ULN and total bilirubin > 2 × ULN
- Any treatment-related liver function test (LFT) abnormality that meets the following criteria, require discontinuation:
 - AST or ALT >5 x ULN in patients with AST/ALT level within normal limits at baseline
 - AST or ALT >10 \times ULN in patients with AST/ALT level more than 1 and up to 3 times ULN at baseline
 - Total bilirubin >3 x ULN irrespective of baseline levels

- Concurrent AST or ALT \geq 3 \times ULN and total bilirubin > 2 \times ULN, irrespective of baseline levels
- Any Grade 4 treatment-related AE or laboratory abnormality, except for the following events which DO NOT require discontinuation:
 - Grade 4 amylase or lipase abnormalities that are not associated with symptoms or clinical manifestations, or radiographic signs of pancreatitis.
 - Isolated grade 4 electrolyte imbalances/abnormalities that are not associated with clinical sequelae and are corrected with supplementation/appropriate management within 72 hours of their onset.
 - Grade 4 lymphopenia and leukopenia.
 - Grade 4 treatment-related endocrinopathy adverse events, such as ACTH deficiency, hyper- or hypothyroidism, or glucose intolerance, which resolve or are adequately controlled with physiologic hormone replacement (corticosteroids, thyroid hormones) or glucose-controlling agents, respectively, may not require discontinuation after discussion with and approval from the Sponsors.
- Grade 3 and 4 adrenal insufficiency require discontinuation
- Any dosing interruption lasting >6 weeks, with the following exceptions: NOTE: Dosing interruptions >6 weeks that occur for non-drug-related reasons as well as for treatment of related AEs and subsequently tapering of steroids may be allowed if approved by the IND Sponsor. Patients must have had no recurrence of symptoms or new symptoms during steroid taper.

New immune related events or exacerbation of existing events during steroid treatment or taper suggest the presence of ongoing immune activation and should require permanent discontinuation.

• Any subjects who require additional immune suppressive treatment beyond steroids should go off study treatment

If nivolumab has to be permanently discontinued because drug-related toxicity, the patient will be permanently discontinued from entinostat treatment too.

In the case that a participant develops intolerance or side effect that is attributable to entinostat, the participant may, at his or her discretion, continue to receive only Nivolumab as otherwise indicated as long as they have received at least 1 full dose of both entinostat and nivolumab and nivolumab re-treatment criteria are met as outlined above.

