4.3 Definition of Unacceptable Toxicities

Unacceptable toxicities are defined as treatment-related:

• Grade 3 or greater non-hematologic toxicities. Exceptions include:

- Grade 3 nausea/vomiting if improved to Grade 2 levels or better within 72 hours
- Asymptomatic laboratory abnormalities
- Grade 3 fatigue
- Grade 3 dermatologic AEs that are considered mild in severity but only considered grade 3 because of >30% body surface involvement
- Grade 3 pruritus
- Grade 3-4 hyperglycemia or grade 3 endocrinopathies where symptoms are controlled on hormone replacement therapy
- Febrile neutropenia Grade 3 or Grade 4:
 - Grade 3 is defined as ANC <1.0×109/L with a single temperature of >38.3°C (101°F) or a sustained temperature of ≥38°C (100.4°F) for more than 1 hour
 - Grade 4 is defined as ANC <1.0×109/L with a single temperature of >38.3°C (101°F) or a sustained temperature of \geq 38°C (100.4°F) for more than 1 hour, with life-threatening consequences and urgent intervention indicated.
- Grade 4 thrombocytopenia (i.e., platelet count <25×109/L)
- Grade 3 thrombocytopenia with clinically significant bleeding
- Any other toxicity resulting in a dose reduction in therapy (at the discretion of the IND Sponsor)

• Failure to complete all protocol specified treatment doses (at the discretion of the IND Sponsor) • Concurrent elevation of transaminases and bilirubin consistent with Hy's Law criteria Note: The original Hy's Law parameters for treated patients relative to comparator patients have been broadened over time (Kaplowitz and DeLeve 2003, Zimmerman 1999) to include additional parameters, but still require that these 3 criteria be met:

i. injury: elevation of >3×ULN ALT or AST activity; and ii.function: >2×ULN total bilirubin (another clinical marker for function, such as >1.5×ULN INR may be acceptable if the change is clinically significant in the absence of obstruction) without >2×ULN alkaline phosphatase (ALP); and iii.clinical verification to ensure effect is health product-induced and not induced by disease or another cause of injury.

• Grade 5 toxicity

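### On the visible text, 5.1.4 calls for stopping nivolumab for asymptomatic grade 3 amylase/lipase lasting over 7 days but exempts the same finding at grade 4

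*Combined protocol and SAP*

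**What the plan says.** Section 5.1.4 of the combined protocol and SAP lists the criteria for discontinuing nivolumab. The grade 3 criterion reads "Any Grade 3 non-skin, drug-related AE lasting > 7 days, with the following exceptions". Its exceptions are a group of events that stop treatment at any duration, endocrinopathies controlled on hormone replacement, and fatigue with a 14-day limit.

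The grade 4 criterion has a wider opening: "Any Grade 4 treatment-related AE or laboratory abnormality, except for the following events which DO NOT require discontinuation". Its exemptions include "Grade 4 amylase or lipase abnormalities that are not associated with symptoms or clinical manifestations, or radiographic signs of pancreatitis" and "Grade 4 lymphopenia and leukopenia".

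Three other sections bear on the same events:

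- Section 5.1 (nivolumab dose delay) says that, at grade 3 or higher, a "drug-related amylase or lipase abnormality that is not associated with symptoms or clinical manifestations of pancreatitis does not require dose delay". It also exempts grade 3 lymphopenia from delay.
- Section 4.3 counts as unacceptable "Grade 3 or greater non-hematologic toxicities. Exceptions include", and one of those exceptions is "Asymptomatic laboratory abnormalities".
- Section 6.3 has all grade 3 and 4 laboratory results that worsen from baseline reported as AEs.

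Under 4.8 and 5.1.4, permanently stopping nivolumab for drug-related toxicity also stops entinostat. A patient whose event is attributed to entinostat may instead continue on nivolumab alone, subject to stated conditions.

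**The concern.** A stopping rule should not be stricter for the milder grade of the same abnormality. Read together, 5.1.4 and 6.3 produce that result. A patient with drug-related, symptom-free grade 3 lipase for more than 7 days is dosed on schedule under 5.1 and falls within the 4.3 exception, yet meets the grade 3 stop in 5.1.4. If the value rises to grade 4 without symptoms or signs of pancreatitis, the same section does not require stopping.

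At stake is whether that patient keeps study treatment. Section 5 does not allow nivolumab dose reduction, so there is no intermediate step on that drug, and a nivolumab stop for toxicity ends entinostat as well. Discontinuations are also among the data reviewed under 6.12. The text gives two opposite answers for one patient, and different investigators could resolve it differently.

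**Working it through.** The plan states no figure to reproduce. The check sets the rules side by side for each abnormality.

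**Step 1: does a grade 3 laboratory value fall under the grade 3 bullet?** The bullet covers AEs and excludes only skin events. Section 6.3 has worsened grade 3 and 4 laboratory results reported as AEs, and reserves its clinical-significance test for grades 1 and 2. Section 5.1 writes a non-laboratory restriction into its grade 2 delay rule, but 5.1.4 has no such word. Read literally, the value is covered if it is drug-related.

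**Step 2: compare the grades (drug-related events, literal reading).**

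| Abnormality | Grade 3, more than 7 days | Grade 4 |
|---|---|---|
| Amylase/lipase without symptoms or signs of pancreatitis | No delay (5.1); stop (5.1.4 with 6.3) | No delay (5.1); no stop (5.1.4) |
| Lymphopenia | No delay (5.1); stop | Delay (only grade 3 is exempt in 5.1); no stop |
| Leukopenia | Delay (5.1); stop | Delay (5.1); no stop |

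The first row is a clean conflict. The other two are weaker: grade 4 is delayed, and an interruption of more than 6 weeks is itself a reason to stop unless the IND sponsor approves continuing.

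**Step 3: what happens to entinostat?** If nivolumab is stopped for drug-related toxicity, entinostat stops too. If the event is attributed to entinostat, 4.8 and 5.1.4 let the patient continue on nivolumab alone. That route spares nivolumab, not entinostat.

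**Step 4: can the 7-day condition be met on the calendar?** Amylase and lipase are in the chemistry panel (Section 10, note 7), drawn on Days 1 and 15, each ±3 days.

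- Shortest gap: (15 − 3) − (1 + 3) = 12 − 4 = 8 days
- Nominal gap: 15 − 1 = 14 days
- Longest gap: (15 + 3) − (1 − 3) = 18 + 2 = 20 days

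Two consecutive grade 3 values are therefore at least 8 days apart. If the abnormality is assumed continuous between them, it exceeds 7 days. This shows only that the rule is reachable, because the documents give no event rates.

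**The case against.** The strongest reply is that the authors meant the grade 3 bullet to leave laboratory values out. Several texts support this:

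- Thrombocytopenia has its own rule, "Grade 3 treatment-related thrombocytopenia > 7 days OR that is associated with bleeding requires discontinuation". Apart from the bleeding limb, it would be redundant if the general bullet already covered laboratory values. Liver tests also have their own rules.
- Laboratory abnormalities are named beside AEs in the grade 4 bullet but not in the grade 3 bullet. Sections 5.1 and 5.1.2 also list the two as separate items.
- Section 6.2.1 says that laboratory findings without clinical significance are in general not recorded as AEs.
- Section 6.3 is a reporting rule. It ends by leaving to the investigator whether an AE is related and severe enough to take the patient off treatment. Its definition of related also requires that no other cause be identified, which can narrow the trigger in pancreatic cancer.
- Section 4.5.1 sends related AEs of grade 2 or higher to the PI and IND sponsor at once. For events present at baseline, Section 5 lets the investigator act on the grade shift.

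Most of this stands as evidence of intent, and it softens the consequence. A reader might infer that the plan forces the stop with no room for judgment. The close of 6.3 and the discussion required by 4.5.1 do not support that. But none of these texts writes the exemption, whereas 5.1 and 4.3 write theirs out.

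Sections 5.1.3 and Appendix D are the natural places for laboratory management and are not visible, so no claim is made about what they contain.

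**Conclusion.** The point holds as a minor drafting correction. On the visible text there is one clean conflict (asymptomatic amylase/lipase) and two weaker grade inversions (lymphopenia and leukopenia). It rests on reading 6.3 into 5.1.4, on the event being judged drug-related, and on nothing in 5.1.3 or Appendix D resolving it.

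Three stronger readings are not supported:

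- A reader might infer an effect on ORR or power. The documents give no event rates, and none is claimed.
- A reader might set the 7-day limit at grade 3 against the 6-week limit on interruptions at grade 4. These are different clocks, AE duration and length of dosing interruption, so their difference is not a meaningful size.
- A reader might infer that every grade 3 laboratory value lasting more than 7 days is meant to be a stop. The wording elsewhere points the other way.

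**What to change.** Add one exception to the grade 3 bullet in 5.1.4. It should say that discontinuation is not required for grade 3 amylase or lipase elevation without symptoms, clinical manifestations or radiographic signs of pancreatitis, or for grade 3 lymphopenia or leukopenia.

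Have the sponsor state at the same place whether the bullet covers any other laboratory abnormality beyond the separate thrombocytopenia and liver-test rules. Naming three exceptions without that statement could imply that all other grade 3 laboratory values lasting more than 7 days are stops, which the authors probably did not intend. Section 6.1.1 lists hypoalbuminemia, hypophosphatemia and anemia as common with entinostat, so this matters.

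Cost: one line in a protocol amendment, plus the sponsor's statement. No extra patients, visits or tests.
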